# 6. Data collection

### Multiple Choice Questionnaire (MCQ)

MCQ's will be distributed by email to participating GPs at 3, 6, 9, and 12 months. The email includes a link to an online questionnaire prepared and collected using Forms (Microsoft Office, Redmond, USA). A reminder will follow after two weeks to participants failing to complete the MCQ after the initial invitation. Data will be transferred and saved on a secure server at Aalborg University.

### Assessment of scanning competence

The assessment of participants scanning competence using the OSAUS score will be performed in the same manner using the same expert assessors at baseline and after 14 months.

During the assessment, only the participant and the assessor are present. Each assessment will follow the same structure, where experts will assess the participants by asking the following questions:

In which clinical scenarios would you perform this POCUS examination (Item 1 in the OSAUS)

The experts will ask participants to demonstrate the POCUS examination (for maximum five minutes) to assess the following:

- Applied knowledge of the ultrasound equipment (Item 2 in the OSAUS)
- Image optimization (Item 3 in the OSAUS)
- Systematic examination (Item 4 in the OSAUS)
- Interpretation of images (Item 5 in the OSAUS)

The experts will present the participants with a picture of common pathology and ask the participants the following questions:

- How would you interpret these ultrasound findings? (Item 6 in the OSAUS)
- If you were to describe this examination in the medical record, what would you write? (Item 6 in the OSAUS)
- What would you do if you found it? (Item 7 in the OSAUS)

Following the assessment, the participant will receive feedback on the level of performance and educational advice. The total duration of the assessment is expected to last 90 minutes for each participant. The assessor completes an OSAUS score for each of the ten examinations performed by the participant.

The OSAUS assessment tool measures competency according to seven key domains: 1) Indication for the examination 2) Applied knowledge of ultrasound equipment 3) Image optimization 4) Systematic examination 5) Interpretation of images 6) Documentation of examination and 7) Medical decision making. Each domain is rated using a five-point Likert scale with descriptions of performance ranging from very poor (score=1) to excellent (score=5).

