
Secondary outcome 11 (S11): For GPs, participating in a POCUS quality assurance program, their evaluation of the program after 12 months..

3 Protocol version

Version 5 November 14th 2022

4 Funding

This study will be conducted as independent research at Center for General Practice at Aalborg University and is financially supported by The Novo Nordisk Foundation (grant number 0061821) and The General Practice Foundation in Denmark (grant number A3495).

5 Roles and responsibilities

5a Names, affiliations, and roles of protocol contributors

[name] (SKA) will be the principal investigator.

SKA, [name] (CAA) and [name] (MBJ) will oversee the choice of and collection of outcome measures.

CAA, SKA and MBJ wrote the first draft of the protocol.

[name] (SLC) will assist in statistical guidance. [name] (AR) will draft the statistical analysis plan.

CAA will handle participant correspondence. AR will handle the data cleansing and do the data analysis.

[name] (OG), MBJ, [name] (LP), [name] (CS) and SKA will perform the OSAUS evaluations of scanning competence at 12 months.

CAA, MBJ, SLC, OG, LP, CS and SKA are all expected to make valuable scientific additions to the draft and will be co-authors on subsequent manuscripts based on these data.

The definition of author is defined on ICMJE's four criteria¹:

Substantial contributions to the conception or design of the work; or the acquisition, analysis, or interpretation of data for the work; AND

Drafting the work or revising it critically for important intellectual content; AND

Final approval of the version to be published; AND

Agreement to be accountable for all aspects of the work in ensuring that questions related to the accuracy or integrity of any part of the work are appropriately investigated and resolved.

The expected author list is: [name], [name], [name], [name], [name], [name], [name], [name].

5b Name and contact information for the trial sponsor

Trial sponsor: Center for General Practice at Aalborg University (CAM AAU)

Contact name: [name]

Address: Center for General Practice in Aalborg, [name]

E-mail: [contact]

5c Role of study sponsor and funders

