Secondary outcome 6 (S6): For GPs, participating in a POCUS quality assurance program, the test scores in the online quiz at months 3, 6, 9 and 12 after baseline.

Secondary outcome 7 (S7): For GPs, participating in a POCUS quality assurance program, the association between OSAUS score at 12 months and total number of performed POCUS examinations for each of the ten scanning modalities included in the curriculum.

Secondary outcome 8 (S8): For GPs, participating in a POCUS quality assurance program, the association between OSAUS score at 12 months and the number of completes quizzes in the quality assurance program.

Secondary outcome 9 (S9): For GPs, participating in a POCUS quality assurance program, the association between OSAUS score at 12 months and the test score in the quizzes in the quality assurance program.

Secondary outcome 10 (S10): For GPs, participating in a POCUS quality assurance program, the association between OSAUS score at 12 months and the OSAUS score at baseline.

Secondary outcome 11 (S11): For GPs, participating in a POCUS quality assurance program, their evaluation of the program after 12 months.

8 Trial design

This is a cohort study designed as a follow-up for a hybrid effectiveness-implementation study (ClinicalTrials.gov Identifier: NCT05274581). In the previous study, 18 GPs attended an ultrasound course targeted to office-based GPs. The ultrasound course consisted of three teaching seminars over three months (Marts – June 2022), a curriculum of 10 POCUS applications, an online learning platform providing educational support before, during and after the teaching sessions (see Figure 1). At the end of the ultrasound course (June 2022) and again 3 months after the ultrasound course (September 2022), all participants had their scanning competences within the 10 POCUS applications assessed by external experts. These experts were blinded to the participants previous experience and learning process. The assessment of scanning competence was done using the OSAUS assessment tool¹⁴. Following this study participants have implemented POCUS in their clinical practice, where they use POCUS as part of the patient examination.

Before data collection starts, this trial will be registered on *clinicaltrials.gov*.

Methods - Participants, interventions, and outcomes

9 Study settings

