(P1): The summarized OSAUS score after 12 months for all ten modalities will be calculated as percentage of maximum score. To summarize normal and non-normal distributed data similarly mean(SD) as well as median(IQR) will be presented together with minimum and maximum scores.

Primary outcome 2 (P2):

The summarized OSAUS score at baseline and at 12 months for each participating GP will be compared and the proportion of GPs, with an OSAUS score at 12 months larger than or equal to the ultrasound competence score at baseline, will be reported.

Secondary outcomes

(S1): For GPs, participating in a POCUS quality assurance program, the OSAUS scores and the item scores after 12 months, for each of the ten scanning modalities included in the curriculum will be calculated and presented as median, IQR, minimum and maximum score.

(S2): We calculate the proportion of GPs, who achieve a minimum OSAUS score of three for all seven domains for each of the ten scanning modalities after 12 months. As variation in scores can occur between the four expert assessors. We will normalize the scores by multiplying a given accessors score with (0.2 x sum of scores of all five accessors/the given accessors mean score) prior to calculating the proportion of successful GPs.

For the secondary outcome S3, we will use the GPs assessment of their own scanning competence. The GPs will declare to which degree they have POCUS scanning competence within a specific scanning modality to perform the scan un-supervised in general practice (To a very high degree, to a high degree, to some degree, to a lesser degree, not at all, unsure).

(S3): We calculate the proportion of GPs, who rate themselves as competent to perform POCUS un-supervised in general practice, after the educational period (three months after baseline), within each of the ten scanning modalities.

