Our potential study population is the 18 GPs who participated in the ultrasound course organized by PLO-e. We expect a participation rate of 80% corresponding to 15 GP.

With 15 participants the total number of possible completed 7-item OSAUS questionnaires will be 15 for each modality and 150 for the combined estimate after 12 months. This is considered sufficient to estimate mean estimates and provide confidence intervals with acceptable spread.

15 Recruitment

All participants, who attended the PLO-e ultrasound course were invited to participate in the study. The ultrasound course was listed in PLO-e course catalogue for 2022 and as such offered to all GP working in primary care in Denmark.

Assignment of interventions

16a Allocation Sequence generation

n/a

16b Allocation concealment mechanism

n/a

16c Implementation

n/a

17 Blinding

Expert assessors performing the competence assessment (primary outcomes) have a medical background and are considered experts in the field. They have not been teaching participants in the training program. They will be blinded to the participants prior experience with POCUS, the

number of performed POCUS examinations, and any other elements in the participants' learning process.

The principal investigator (SKA) and MBJ acts as expert assessors in this study and as such, they will be blinded to the background information on participants, the data collection and the analysis of data. CAA will be in charge of all participant correspondence, AR will be cleaning the data set and analyzing the data.

Data collection, management, and analysis

18 Data collection - Plans for assessment and collection of outcome, baseline, and other trial data

Multiple Choice Questionnaire (MCQ)

MCQ's will be distributed by email to participating GPs at 3, 6, 9, and 12 months. The email includes a link to an online questionnaire prepared and collected using Forms (Microsoft Office, Redmond, USA). A reminder will follow after two weeks to participants failing to complete the MCQ after the initial invitation. Data will be transferred and saved on a secure server at Aalborg University.

Assessment of scanning competence

The assessment of participants scanning competence using the OSAUS score will be performed in the same manner using the same expert assessors at baseline and after 12 months.

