# 1. Overview of analysis

This document contains the statistical analysis plan for "Can a tailored quality assurance program help general practitioners maintain POCUS scanning competence?: A cohort study from Denmark". The study protocol (ClinicalTrials.gov ID NCT05625646) specified the intended analyses *prior to collection of the primary outcome*. This document elaborates on these intended analyses to be performed in the main study paper.

This study is a follow-up of a prior study (ClinicalTrials.gov ID NCT05274581) in which 18 general practitioners completed a tailored ultrasound educational program and had their ultrasound scanning competences assessed immediately after the program and at follow-up after three months. The three-month follow-up in the previous study is baseline for the present study.

Hence, data for the present study were gathered between September 7th 2022 and January 22nd 2024. Scanning competence scores were collected at baseline (September 7th and November 3rd 2022) and after 14 months (November 30th 2023 and January 22nd 2024). Quarterly quizzes were collected in: December 2022/January 2023(Quiz 1), March/April 2023(Quiz 2), August/September 2023(Quiz 3) and October/November 2023(Quiz 4). Remuneration fess for performed ultrasound scans were collected between November 2022 and November 2023. Background characteristic on participating general practitioners were collected on March 3rd 2022 when participants enrolled in the previous study and updated for the present study.

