### Education of POCUS expert assessors

The POCUS expert assessors all have prior experience using the OSAUS score. Still, prior to the assessment of the participants' performance in this study, the POCUS experts participate in a 90-minutes online training session with CAA who has prior experience with the education of a team of assessors. During this training session, the POCUS experts are presented to the OSAUS score and the procedure for assessing the participants in this study. The POCUS experts are instructed to rate according to the standard expected from a GP, who is capable of performing POCUS unsupervised in general practice.

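### SAP 9 sets every expert to the same average without separating the visits; if expert workloads differ between visits, this shrinks the adjusted P2 change toward zero.

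*SAP*

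**What the plan says.** SAP 5.1 defines P2 as a within-GP comparison of two visits. It reports the mean difference in OSAUS sum score and the proportion of GPs whose follow-up score is at least their baseline score. SAP 1 fixes the starting point: "The three-month follow-up in the previous study is baseline for the present study".

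Both documents say the panel is constant. Protocol 18 has the assessment done "using the same expert assessors at baseline and after 12 months"; SAP 6 repeats this as "using the same expert assessors at baseline and after 14 months". Neither gives the number of GPs that each assessor scores at each visit.

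SAP 9 analyses OSAUS scores by linear regression or repeated measures ANOVA with participant as random effect. For interrater variation it calculates a mean for each expert and adjusts so that all experts end up with an equal mean. The visits over which the mean is taken are not stated. Raw complete-case results are tabulated next to results that include imputation and the expert adjustment, and SAP 9 describes the latter set as statistically optimal.

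**The concern.** The study has one group and two visits, and its aim is to show that competence is maintained. An expert's mean depends on how lenient the expert is and also on which visit most of that expert's scores come from. If true scores fall over time, an expert who worked mainly at follow-up has a low mean for that reason alone. Forcing that mean up to the common level, and pulling down the mean of an expert who worked mainly at baseline, removes part of the fall.

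At stake is the adjusted P2 mean change. The proportion of GPs at or above baseline is also exposed wherever it is computed from adjusted scores. A fall that is understated reads as maintenance.

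**Working it through.** **Inputs.** N = 15 GPs (Protocol 14, SAP 7): 18 x 0.80 = 14.4, rounded up to 15, and 15 x 10 modalities = 150 forms, so the plan's own figures reproduce. Five assessors are listed in Protocol 5a and 10. The documents give no rater effect, standard deviation or workload. The following are therefore assumptions: a true fall from 80% to 70% of maximum, no leniency differences at all, expert means pooled over both visits, and the workloads shown.

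**Same five assessors, unequal workloads.** Let an expert score b GPs at baseline and f at follow-up. The expert's pooled mean is (80b + 70f)/(b + f). The grand mean is 75, so the shift applied is 75 minus the expert's mean.

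| Expert | b | f | Pooled mean | Shift |
|---|---|---|---|---|
| A | 5 | 1 | 78.33 | -3.33 |
| B | 4 | 2 | 76.67 | -1.67 |
| C | 3 | 3 | 75.00 | 0 |
| D | 2 | 4 | 73.33 | +1.67 |
| E | 1 | 5 | 71.67 | +3.33 |

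- Adjusted baseline mean: 80 + (5(-3.33) + 4(-1.67) + 3(0) + 2(1.67) + 1(3.33))/15 = 80 - 1.11 = 78.89.
- Adjusted follow-up mean: 70 + (1(-3.33) + 2(-1.67) + 3(0) + 4(1.67) + 5(3.33))/15 = 70 + 1.11 = 71.11.
- Adjusted change: 71.11 - 78.89 = **-7.8**, although no assessor is more lenient than another.

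**General form.** The share of the true change that is removed is (1/(2N)) x sum of (f - b)^2/(f + b) over experts. Here it is (16 + 4 + 0 + 4 + 16)/6 divided by 30 = 0.222, so 77.8% of the change survives. The share cannot be negative and is zero only when b = f for every expert. A true -5 would appear as 0.778 x (-5) = -3.9.

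**Range over workloads, true change -10.**
- Any pattern with b = f for every expert: -10, no bias.
- 3/3/3/3/3 at baseline and 0/4/4/4/3 at follow-up: (9/3 + 3 x 1/7 + 0)/30 = 0.114 removed, giving -8.9.
- 5/4/3/2/1 and then 1/2/3/4/5: -7.8.

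**If some assessors scored only at follow-up** (a hypothetical that the documents do not support), with k GPs scored by them and the returning assessors otherwise alike: the returning assessors' mean is m = (15 x 80 + (15 - k) x 70)/(30 - k), and the adjusted change is -10 + (k/15)(m - 70). This gives -8.9, -7.5 and -5.7 for k = 3, 6 and 9, and 0 for k = 15.

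**Check of the alternative.** In the table's example every score equals 80 minus 10 at follow-up, plus zero for expert. A model with visit and expert together fits this exactly, so it returns -10 whenever the two effects are separable. A simulation with these workloads gave about -10.0 for the joint model and -7.8 for the equal-average rule.

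**The case against.** The strongest defence is that both documents state that the same assessors were used. With five assessors and 15 GPs an even split is three each (15/5), and if that held at both visits there is no bias. SAP 9 also does not say that the averages are pooled. The raw results appear beside the adjusted ones, and in the example they still show -10, so the adjustment could not hide the fall. The shrinkage is also not always favourable: a true gain would be understated in the same proportion.

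All of this stands, and it makes the bias conditional. It does not remove the problem, because a constant panel does not guarantee constant workloads, and SAP 9 leaves the pooled reading open. A reading by visit is not automatically safe either. If experts are set to one common value at each visit, the mean change is zero by construction.

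A reader might go further and infer that the raters themselves changed. The documents do not support that:

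- Protocol 8 has the earlier scores "assessed by external experts", and two of the five assessors are study investigators. But Protocol 17 says the assessors did not teach the course, so the word can mean external to the teaching. It is unclear, not contradictory.
- Protocol 5a says the five listed assessors "will perform the OSAUS evaluations of scanning competence at 12 months". Baseline came from the previous study, so assigning only the remaining assessment is expected.
- The S2 paragraph of Protocol 12 says "As variation in scores can occur between the four expert assessors", and its next sentence counts five. Both counts concern the 12-month scores. This is a separate slip and no evidence about baseline.
- SAP 6 says that "prior to the assessment of the participants' performance in this study, the POCUS experts participate in a 90-minutes online training session". No training date is given, so it cannot be placed between the two visits.

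**Conclusion.** The point holds in a limited form. The equal-average rule in SAP 9 can absorb part of the time effect that P2 is meant to measure. It does so when expert means are pooled over visits and at least one expert scored different numbers of GPs at the two visits. Under the assumed true change of -10 points in 15 GPs, the unequal workloads tried for an unchanged panel give -8.9 and -7.8; balanced workloads give -10. Only the adjusted results are affected.

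The actual size cannot be derived, because the documents give neither workloads nor the visits over which the means are taken. The inference that P2 reflects a change of raters is not supported, since both documents say the assessors were the same. A better method is available at little cost, so the change is worth making.

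**What to change.** In SAP 9, replace the equal-average rule with one model of OSAUS score that contains visit, expert and a participant effect. Take the adjusted P2 mean change and the expert-corrected scores from that model. SAP 9 already plans a model with participant as random effect, so this is a small extension.

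Do not set experts to one common mean within each visit, because that erases the change. Centring on each visit's own mean would keep the overall change. But where each GP keeps the same assessor, it would force every assessor's GPs to the same average change and so distort the P2 proportion.

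Add a sensitivity analysis of P2, on unadjusted scores, in GPs scored by the same assessor at both visits. In these GPs constant leniency cancels.

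Cost: new wording in SAP 9 and slightly more analysis work. The assessors fill in the score sheets themselves (Protocol 19), so who scored whom should be recoverable. The same-assessor subset is smaller and less precise. If it turns out that no assessor scored at both visits, expert and visit cannot be separated by any model, and the report should state this as a limitation.

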### Education of POCUS expert assessors

The POCUS expert assessors all have prior experience using the OSAUS score. Still, prior to the assessment of the participants' performance in this study, the POCUS experts participate in a 90-minutes online training session with CAA who has prior experience with the education of a team of assessors. During this training session, the POCUS experts are presented to the OSAUS score and the procedure for assessing the participants in this study. The POCUS experts are instructed to rate according to the standard expected from a GP, who is capable of performing POCUS unsupervised in general practice.

### Self-rated scanning competence

In relation to the expert assessment of scanning competence, participants were asked to fill out a questionnaire where they declare whether or not they have POCUS scanning competence within this scanning modality to perform the scan un-supervised in general practice. The expert assessors were blinded to this declaration.

### **Evaluation questionnaire**

After 12 months following the final MCQ-quiz and the final evaluation of scanning competence, we will circulate an evaluation questionnaire for participants. This questionnaire will be developed based on collected experiences during the study.

# 7. Sample size

Our potential study population is the 18 GPs who participated in the ultrasound course organized by PLO-e. We expect a participation rate of 80% corresponding to 15 GP.

With 15 participants the total number of possible completed 7-item OSAUS questionnaires will be 15 for each modality and 150 for the combined estimate at follow-up.

# 8. Safety committee

A steering committee affiliated with CAM AAU (TL, UM, TMJ, SKA, MBJ and CAA) will handle and oversee the development of the quality assurance tool.

A safety committee will be set up to handle all reports of adverse and suspected adverse events (AEs) and serious adverse events (SAEs). MBJ will head the committee

# 9. Statistical analysis

The analysis of OSAUS sum scores and item scores will be performed using linear regression or repeated measures ANOVA, with participants being the random effect. Cohen's d will be used to estimate effect size. To account for interrater variation, we will calculate an average score for each expert and adjusted results so that experts have the same average score. Sensitivity analyses will be performed and the results of both complete case and adjusted analyses will be reported. Distributions of baseline values will be presented as mean (SD) and median [IQR] for continuous or n (%) for categorical variables. Fisher's exact test will be used to compare out sample to the general population of GPs in Denmark. OSAUS scores will be presented in tables as summarized complete case (raw data) and statistical optimal data (including imputation and adjustment for expert variation). Results with p-values < 0.05 will be considered statistically significant. All statistical analyses will be performed using STATA version 18 (StataCorp, Texas, USA).

